3.2 STUDY OBJECTIVES

3.2.1 Primary Objective

The primary trial objective is to carry on from the AP-003-C main study (one injection) and evaluate the safety of a 4-mL intra-articular (IA) injection of Ampion™ with repeat dosing every 12 weeks for 52 weeks and/or with five total injections of Ampion™.

3.2.2 Exploratory Objectives

The exploratory objectives are to analyze the efficacy of a 4-mL intra-articular (IA) injection of Ampion™ with repeat dosing every 12 weeks for 52 weeks and/or with five total injections of Ampion™.

3.3 SAFETY MONITORING COMMITTEE

A Safety Monitoring Committee (SMC) will be established to review the safety of Ampion™ as the study progresses. The SMC will consist of independent clinicians not involved in the clinical trial, the Medical Monitor and Ampio Pharmaceuticals, Inc. representatives. The SMC will be primarily responsible for reviewing any serious Adverse Event (SAE) and other clinically important safety findings (e.g., discontinuations due to AEs) that may occur during the study. A charter will be developed to detail the SMC review responsibilities, the frequency of meetings, and data evaluation plans.

3.4 STOPPING RULES

The entire study may be stopped under defined circumstances as outlined in Section 7.

3.5 STUDY ENDPOINTS

3.5.1 Primary Endpoint

- Evaluate the incidence and severity of treatment-emergent adverse events (TEAEs)

3.5.2 Exploratory Endpoints

- Responder status based on the OMERACT-OARSI responder criteria
- Evaluate OMERACT-OARSI ‘controlled’ responder defined as a 20% improvement in Pain and Function and 0.5 point absolute change in the 5-point Likert Scale
- Evaluate 20% improvement in PGA and 0.5 point absolute change in the 5-point Likert Scale
- Mean change and percent change in WOMAC A pain subscore
- Mean change and percent change in WOMAC B stiffness subscore
- Mean change and percent change in WOMAC C physical function subscore
- Mean change and percent change in PGA
- Mean Change and percent change in WOMAC A pain subscore questions 1 and 2 (pain with movement)
- Mean Change and percent change in WOMAC A pain subscore questions 3–5 (resting pain)
- Change in contralateral knee pain (WOMAC A)
- Change in contralateral knee stiffness (WOMAC B)
- Change in contralateral knee function (WOMAC C)
- Time to Total Knee Replacement (TKR)
- Use of rescue analgesia (amount of acetaminophen used)

3.6 BLINDING AND RANDOMIZATION

All subjects will receive Ampion 4-mL which is provided in study kits. Each kit will contain labeled vials, a syringe, a needle and rescue medication.

4 SELECTION OF SUBJECTS

4.1 NUMBER OF SUBJECTS

A total of approximately 161 subjects will be enrolled from the AP-003-C main study into the AP-003-C-OLE study.

4.2 INCLUSION CRITERIA

1. Participation and completion in the AP-003-C study
2. Able to provide written informed consent to participate in the study
3. Willing and able to comply with all study requirements and instructions of the site study staff
4. Male or female, 40 years to 85 years old (inclusive), as assessed in the AP-003-C main study
5. Must be ambulatory, as assessed in the AP-003-C main study
6. Study knee must have a clinical diagnosis of OA and supported by radiological evidence (Kellgren Lawrence Grade 4) as assessed in the AP-003-C main study.
7. Moderate to moderately-severe OA pain in the index knee (rating of at least 1.5 on the WOMAC Index 3.1 5-point Likert Pain Subscale), as assessed in the AP-003-C main study
8. Moderate to moderately-severe OA function in the index knee (rating of at least 1.5 on the WOMAC Index 3.1 5-point Likert Function Subscale), as assessed in the AP-003-C main study
9. WOMAC A, 5-point Likert pain subscale <1.5 in the contralateral knee, as assessed in the AP-003-C main study
10. Ability to discontinue NSAID ± 72 hours before/after injections (in-office visits). Low-dose Aspirin (81 mg) is allowed during the study but must not be taken at least 24 hours prior to in-office visits.
11. No analgesia (including acetaminophen [paracetamol]) taken 24 hours prior to an efficacy measure

4.3 EXCLUSION CRITERIA

Subjects fulfilling one or more of the following criteria may not be enrolled in the study:

1. As a result of medical review and screening investigation, the Principal Investigator considers the subject unfit for the study
2. Known clinically significant liver abnormality (e.g. cirrhosis, transplant, etc.)
3. A history of allergic reactions to human albumin (reaction to non-human albumin such as egg albumin is not an exclusion criterion)
4. A history of allergic reactions to excipients in 5% human albumin (N-acetyltryptophan, sodium caprylate)
5. Presence of tense effusions

6. Inflammatory or crystal arthropathies, acute fractures, history of aseptic necrosis or joint replacement in the affected knee
7. Isolated patella femoral syndrome, also known as chondromalacia
8. Any other disease or condition interfering with the free use and evaluation of the index knee for the duration of the trial (e.g. cancer, congenital defects, spine OA)
9. Major injury to the index knee within the past 12 months
10. Severe hip OA ipsilateral to the index knee
11. Any pain that could interfere with the assessment of index knee pain (e.g. pain in any other part of the lower extremities, pain radiating to the knee)
12. Any pharmacological or non-pharmacological treatment targeting OA started or changed during the 4 weeks prior to enrollment in the OLE study or likely to be changed during the duration of the study
13. Pregnancy or planning to become pregnant during the study
14. Use of the following medications:
 - a. No IA injected pain medications in the study knee during the study. HA and steroid injections in the contralateral knee (non-study knee) are acceptable while on study except \pm 14 days of an Ampion™ injection in the study knee.
 - b. No analgesics containing opioids.
 - c. NSAIDs are not permitted \pm 72 hours before/after IA injections (in-office visits); acetaminophen is available as a rescue medication during the study from the provided supply.
 - d. No topical treatment on the study knee during the study
 - e. No significant anticoagulant therapy (e.g. Heparin or Lovenox) during the study (treatment such as Aspirin and Plavix are allowed)
 - f. No systemic treatments that may interfere with safety or efficacy assessments during the study
 - g. No immunosuppressants
 - h. No use of corticosteroids
 - i. No human albumin treatment in the 3 months prior to the AP-003-C main study or interim period prior to enrollment into the OLE study. No human albumin treatment throughout the duration of the OLE study.

4.4 INCLUSION OF SUBJECTS INCAPABLE OF GIVING INFORMED CONSENT

No subject incapable of giving informed consent may be enrolled in the study.

5 STUDY PLAN AND PROCEDURES

Subjects will receive an IA injection of Ampion™ at Visit 9, Visit 11, Visit 13 and Visit 15 of AP-003-C-OLE. Telephone contact will be made with the subject 24 hours after each IA injection. The subject will be followed until Visit 17. Safety of repeat injections every 12 weeks for 36 weeks will be evaluated during every visit (in-clinic and telephone); in office-visits will evaluate vital signs, physical exam, adverse events, and blood tests (Visit 17 or Early Termination Visit 18 only). Clinical effects of treatment on OA pain will be evaluated during in-clinic visits at Visit 9, Visit 11, Visit 13, Visit 15 and Visit 17 using the WOMAC osteoarthritis Index 3.1 (pain subscore, stiffness subscore and function subscore) and an overall global severity assessment (Patient's Global Assessment [PGA]). The WOMAC will also be utilized to assess the contralateral knee pain at Visit 9 and Visit 17 (or Early Termination Visit).

The assessments and procedures performed at each subject visit or contact are described in Section 5.1 Description of Study Visits and in Table 6.1, Schedule of Assessments and Procedures.

5.1 DESCRIPTION OF STUDY VISITS

5.1.1 Visit 9 (day -170 to Day 0, in-clinic); Enrollment

The following procedures will be performed at Visit 9 (Day 0):

- Obtain written informed consent for AP-003-C-OLE study before the start of any study specific procedure.
- Review medical history including all previous treatments for OA.
- Evaluate for any AEs ongoing from AP-003-C main study and/or new AEs pre-injection.
- Record prior and concomitant medications including start/stop dates, indication, dose and frequency.
- Record demographic data including year of birth, age, gender and race.
- Measure and record height and weight.
- Obtain hCG urine analysis for women of child-bearing potential
- Perform and record physical examination (prior to injection)
- Record Kellgren Lawrence Grade from radiological assessment, as assessed in AP-003-C main study.
- Complete the WOMAC Index 3.1. for the study knee (prior to injection)
- Complete the WOMAC Index 3.1 for the contralateral knee (prior to injection)
- Complete the PGA for the study knee (prior to injection)
- Evaluate all inclusion and exclusion criteria to ensure that subjects meet all inclusion criteria and none of the exclusion criteria.

- Record vital signs. (Measure body temperature, systolic / diastolic blood pressure [BP] and pulse rate) pre- and post-injection.
- Perform intra-articular injection of study drug.
- Record post-injection AEs if observed.
- Record concomitant medications.
- Issue rescue medication (acetaminophen [paracetamol]).

5.1.2 Visit 10 (24 hours following Visit 9, post-injection follow-up telephone call)

The following procedures will be performed at Visit 10

- Record AEs.
- Record concomitant medications.
- Review rescue medication use.

5.1.3 Visit 11 (Day 84 ± 14 days, in-clinic); Week 12

The following procedures will be performed at Visit 11:

- Perform and record physical examination.(prior to injection)
- Record vital signs. (Measure body temperature, systolic / diastolic blood pressure [BP] and pulse rate) pre- and post-injection.
- Complete the WOMAC Index 3.1. for the study knee (prior to injection)
- Complete the PGA for the study knee (prior to injection)
- Perform intra-articular injection of study drug.
- Record post-injection AEs if observed.
- Record concomitant medications.
- Review/Issue rescue medication (acetaminophen [paracetamol]).

5.1.4 Visit 12 (24 hours following Visit 11, post-injection telephone call)

The following procedures will be performed at Visit 12:

- Record AEs.
- Record concomitant medications.
- Review rescue medication use.

5.1.5 Visit 13 (Day 168 ± 14 days, in-clinic); Week 24

The following procedures will be performed at Visit 13:

- Perform and record physical examination.(prior to injection)
- Record vital signs. (Measure body temperature, systolic / diastolic blood pressure [BP] and pulse rate) pre- and post-injection.

- Complete the WOMAC Index 3.1. for the study knee (prior to injection)
- Complete the PGA for the study knee (prior to injection)
- Perform intra-articular injection of study drug.
- Record post-injection AEs if observed.
- Record concomitant medications.
- Review/Issue rescue medication (acetaminophen [paracetamol]).

5.1.6 Visit 14 (24 hours following Visit 13, post-injection telephone call)

The following procedures will be performed at Visit 14:

- Record AEs.
- Record concomitant medications.
- Review rescue medication use.

5.1.7 Visit 15 (Day 252 ± 14 days, in-clinic); Week 36

The following procedures will be performed at Visit 15:

- Perform and record physical examination.(prior to injection)
- Record vital signs. (Measure body temperature, systolic / diastolic blood pressure [BP] and pulse rate) pre- and post-injection.
- Complete the WOMAC Index 3.1. for the study knee (prior to injection)
- Complete the PGA for the study knee (prior to injection)
- Perform intra-articular injection of study drug.
- Record post-injection AEs if observed.
- Record concomitant medications.
- Review/Issue rescue medication (acetaminophen [paracetamol]).

5.1.8 Visit 16 (24 hours following Visit 15, post-injection telephone call)

The following procedures will be performed at Visit 16:

- Record AEs.
- Record concomitant medications.
- Review rescue medication use.

5.1.9 Visit 17 (Day 280 ± 14 days, in-clinic final visit); Week 40

The following procedures will be performed at Visit 17:

- Perform and record physical examination.

- Record vital signs. (Measure body temperature, systolic / diastolic blood pressure [BP] and pulse rate)
- Complete the WOMAC Index 3.1. for the study knee
- Complete the WOMAC Index 3.1 for the contralateral knee
- Complete the PGA for the study knee
- Record if subject was able to delay TKR by participation in study
- Record AEs if observed.
- Record concomitant medications.
- Draw safety labs
- [Obtain x-ray of study knee](#)
- Review/Collect rescue medication (acetaminophen [paracetamol]).

5.1.10 Early Termination Visit

The following procedures will be performed at Early Termination Visit:

- Perform and record physical examination.
- Record vital signs. (Measure body temperature, systolic / diastolic blood pressure [BP] and pulse rate)
- Complete the WOMAC Index 3.1. for the study knee
- Complete the WOMAC Index 3.1 for the contralateral knee
- Complete the PGA for the study knee
- Record if subject was able to delay TKR by participation in study
- Record AEs if observed.
- Record concomitant medications.
- Draw safety labs
- [Obtain x-ray of study knee \(excluding subjects who terminate in order to receive TKR\)](#)
- Review/Collect rescue medication (acetaminophen [paracetamol]).

5.1.11 Unscheduled Visits

Additional visits may be scheduled at the discretion of the Investigator, for example as part of follow up of AEs.

5.1.12 Missed Visits

Subjects unable to complete a study visit as scheduled should be re-scheduled for a replacement visit as soon as possible. If a subject misses any scheduled follow up visit and cannot be seen prior to the start of the visit range for the next follow up visit, the visit is considered missed.

5.1.13 CONCOMITANT MEDICATIONS

The following medications / therapies are NOT allowed during this clinical study:

1. No IA injected pain medications in the study knee during the study. HA and steroid injections in the contralateral knee are acceptable while on study except \pm 14 days of Ampion injection in the study knee.
2. No analgesics containing opioids.
3. NSAIDS may not be used \pm 72 hours before/after IA injection of Ampion (in-office visits). Low-dose Aspirin (81 mg) is allowed but should not be used at least 24 hours prior to an in-office visit. Acetaminophen is available as a rescue medication during the study from the provided supply.
4. No non-pharmacological treatment targeting OA started or changed during the study.
5. No topical treatment on osteoarthritis study knee during the study.
6. No significant anticoagulant therapy (e.g. Heparin or Lovenox) during the study (treatment such as Aspirin or Plavix is allowed).
7. No systemic treatments that may interfere with safety or efficacy assessments during the study.
8. No immunosuppressants.
9. No use of systemic or intra-articular corticosteroids.
10. No human albumin treatment during the study.

Any medication used during the study should be recorded. All concomitant medication start and stop dates, total daily dose, route, and indication should be recorded.

The provided rescue medication during the 40-week extension study is 500 mg of acetaminophen, 1 tablet every 4 hours as required by the subject, not to exceed 3,000 mg of acetaminophen in a 24-hour period. Dose must be reduced if using other medications that contain acetaminophen (cold medicines, etc.).

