| 
replacement in the affected knee
 
7. Isolated patella femoral syndrome, also known as chondromalacia
 
8. Any other disease or condition interfering with the free use and evaluation of the index knee for the duration of the trial (e.g. cancer, congenital defects, spine osteoarthritis)
 
9. Major injury to the index knee within the last 12 months
 
10. Severe hip osteoarthritis ipsilateral to the index knee
 
11. Any pain that could interfere with the assessment of study knee pain (e.g. pain in any other part of the lower extremities, pain radiating to the knee)
 
12. Any pharmacological or non-pharmacological treatment targeting OA started or changed 4 weeks prior to entry into the AP-003-C-OLE study, or likely to be changed during the duration of the AP-003-C-OLE study
 
13. Pregnancy or planning to become pregnant during the study
 
14. Use of the following medications:
 
a. No IA injected pain medications in the study knee during the study. HA and steroid injections in the contralateral knee (non-study knee) are acceptable while on study except \pm 14 days of an Ampion injection in the study kneeb. No analgesics containing opioidsc. NSAIDs are not permitted \pm 72 hours before/after injections at in-office visits; acetaminophen is available as a rescue medication during the study from the provided supplyd. No topical treatment on the study knee during the studye. No significant anticoagulant therapy (e.g. Heparin or Lovenox) during the study (treatment such as Aspirin and Plavix are allowed)f. No systemic treatments that may interfere with safety or efficacy assessments during the studyg. No immunosuppressantsh. No use of corticosteroidsi. No human albumin treatment in the 3 months prior to the AP-003-C main study or interim period prior to enrollment into the AP-003-C-OLE study. No human albumin treatment throughout the duration of the AP-003-C-OLE study | | |
| 
Test Product, Dose and Mode of Administration:
 
Ampion™ 4-mL intra-articular injection in the knee
 | | |
| 
Reference Therapy, Dose and Mode of Administration:
 
Not applicable
 | | |
| 
Study Duration:
 
40 weeks
 | | |

| Sponsor: Ampio Pharmaceuticals, Inc. | Investigational Product: Ampion™ | Developmental Phase: Phase 3 |
|--|--|--|
| Main Study + Extension Study = 52 weeks | | |
| Criteria for Evaluation: | | |

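### The 72 h NSAID washout is tied to injections, so on its most natural reading Visit 17, the final efficacy visit, has only the 24 h no-analgesia rule

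*Protocol*

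**What the plan says.** - **NSAID rule.** Protocol 5.1.13 item 3 prohibits NSAIDs within "72 hours before/after IA injection of Ampion (in-office visits"). The same 72 h rule appears in inclusion criterion 10 and exclusion criterion 14c, in both the synopsis and Sections 4.2 and 4.3. The synopsis version of 14c reads "72 hours before/after injections at in-office visits".
- **Injections.** Protocol Section 5 places them "at Visit 9, Visit 11, Visit 13 and Visit 15 of AP-003-C-OLE". Section 5.1.9 and Table 6.1 show WOMAC and PGA at Visit 17 but no injection.
- **24 h rules.** Inclusion criterion 11 (Section 4.2) requires no analgesia in the 24 h before an efficacy measure. Item 3 of 5.1.13 adds that low-dose aspirin "should not be used at least 24 hours prior to an in-office visit". Both reach Visit 17.
- **Analyses using Visit 17.** Protocol 10.4.2 takes responder status and score changes from Visit 9 to Visits 11, 13, 15 and 17, and contralateral-knee change from Visit 9 to Visit 17. SAP 4.1 adds differences in pain scores between successive visits and states that there is no comparator.

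**The concern.** The exploratory efficacy results are meant to show whether benefit holds up under repeat injections. With one arm, that depends on scoring subjects under the same conditions at each visit. If NSAIDs are withheld for 72 h before Visits 9 and 15 but only 24 h before Visit 17, part of any change to Visit 17 may reflect residual NSAID effect. A subject who took an NSAID two days before Visit 17 could score lower pain than under the earlier rule, and this would look like maintained benefit. The same applies to the contralateral-knee change, because an oral NSAID acts on both knees.

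**Working it through.** No figure in the plan is at issue, so the check is mainly one of text and timing.

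**1. Rule by visit, injection-only reading.**

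| Visit | Nominal day | Injection | NSAID-free time required before scoring |
|---|---|---|---|
| 9 | 0 | yes | 72 h |
| 11 | 84 | yes | 72 h |
| 13 | 168 | yes | 72 h |
| 15 | 252 | yes | 72 h |
| 17 | 280 | no | 24 h |

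**2. Is that the right reading?** All five statements of the rule name the injection as anchor. Four follow it with a bracket mentioning in-office visits; the fifth (synopsis 14c) says "72 hours before/after injections at in-office visits", which makes the visits the setting of the injections. Item 3 itself uses a purely visit-based rule for aspirin ("should not be used at least 24 hours prior to an in-office visit"), so the authors had that wording available and did not use it for NSAIDs. On the other side, Protocol 10.3.10 says loosely that Ampion is given at each in-clinic visit, which Section 5 and Table 6.1 contradict. The injection-only reading is the better one, but the bracket leaves room for the other.

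**3. Could the post-injection ban from Visit 15 cover Visit 17?** The Visit 15 window is Day 252 ± 14 = 238 to 266. The Visit 17 window is Day 280 ± 14 = 266 to 294. The gap g is nominally 280 − 252 = 28 days, with range 266 − 266 = 0 to 294 − 238 = 56. The period at issue runs from g − 3 to g − 1 days after Visit 15, and the ban ends at day 3. It covers the whole period only if g − 1 ≤ 3 (g ≤ 4) and none of it once g − 3 ≥ 3 (g ≥ 6). On the nominal schedule there is no cover.

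**4. How wide is the exposure?** WOMAC asks about the last 24 h (Protocol 6.1.1), and the 24 h rule is meant to keep that recall period free of analgesics at every visit. What differs at Visit 17 is the preceding 72 − 24 = 48 h, so the only route to bias is carry-over from a dose taken then.

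**5. Which results are touched?** Visit 9 to 17 changes and responder status, and the Visit 15 to 17 successive-visit difference in SAP 4.1. Changes from Visit 9 to Visits 11, 13 and 15 are like with like. The stability analysis in Protocol 10.4.2 compares administration time points, so read strictly it does not involve Visit 17.

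**6. Scale.** The documents give no rate of NSAID use and no residual effect. As an illustration, let u be the share of subjects taking an NSAID 24–72 h before Visit 17 (assumed 10–40%) and d the residual effect on WOMAC A (assumed 0.1–0.3 points, 0–4 scale). Mean shift = u × d:

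- 0.10 × 0.1 = 0.01
- 0.10 × 0.3 = 0.03
- 0.40 × 0.1 = 0.04
- 0.40 × 0.3 = 0.12

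For comparison, take the SD of 0.817 for combined KL 4 Ampion subjects (Protocol Table 1.5.2) and the 100 subjects anticipated in SAP 2.4. The 95% CI half-width for a mean change is 1.984 × 0.817 / √100 = 0.162. That SD comes from single-injection studies and is only a guide. The illustrated shift lies inside sampling error but, unlike sampling error, does not shrink as n grows.

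**The case against.** The strongest reply is that this is a drafting ambiguity with little consequence. The bracket recurs in four places, and with 10.3.10 it suggests that the authors treated injection visits and in-office visits as the same thing. The recall period is already analgesic-free under the 24 h rule. Efficacy is also reported at Visits 11, 13 and 15, so benefit up to Week 36 can be read under a uniform 72 h rule. Visit 17 is in any case 4 rather than 12 weeks after an injection, so the Visit 15 to 17 difference would not be a clean measure of stability even with equal washout. Finally, item 7 prohibits interfering systemic treatment: "No systemic treatments that may interfere with safety or efficacy assessments during the study".

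Much of this stands, and it limits the point to a minor one. It does not remove it. If the bracket was meant to include Visit 17, sites can still read it either way and may apply different rules. Item 7 is general, whereas item 3 deals with NSAIDs by name and restricts them only around injections, so an NSAID taken two days before Visit 17 is not clearly a violation. For the same reason, the per-protocol repeat (Protocol 10.3.3) would not reliably remove such subjects. The difference in time since injection is inherent in the schedule; the difference in washout is avoidable.

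**Conclusion.** The point holds as a minor one. On the better reading of the text, Visit 17 is scored after a shorter NSAID washout than Visits 9, 11, 13 and 15, and the exploratory comparisons in step 5 mix the two conditions. The bias is confined to carry-over from NSAIDs taken 24–72 h beforehand. Its size is unknown; the 0.01–0.12 range rests wholly on assumed inputs. The direction is likely to favour maintained benefit but is not certain: a subject no longer using NSAIDs scores the same under either rule, and the documents say nothing about pain in the first day after stopping. The TEAE primary endpoint is unaffected.

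Three stronger readings are tempting, but the documents do not support them.

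- **That Visit 1 to Visit 17 results are also mismatched.** Visit 1 washout conditions belong to the AP-003-C main study protocol and are not given here.
- **That a planned covariance analysis is compromised.** Protocol 10.4.2 mentions one, but SAP 4.1 makes all analyses descriptive and specifies none.
- **That efficacy is open to uncontrolled drug escalation and needs a table counting such subjects as non-responders.** Item 4 of 5.1.13 does name only half of the entry rule ("No non-pharmacological treatment targeting OA started or changed during the study"). However, exclusion 12 screens out treatment "likely to be changed during the duration of the study", item 7 gives partial cover, and the per-protocol repeat can remove prohibited use. Scoring permitted drug changes as failure is a debatable choice; such a table is optional.

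**What to change.** In Protocol 5.1.13 item 3, inclusion criterion 10 and exclusion criterion 14c (synopsis and body), state that NSAIDs are not allowed for 72 h before every scheduled in-office efficacy assessment, including Visit 17, and for 72 h after each injection. Exempt unplanned Early Termination visits, which often cannot be foreseen three days ahead, and record NSAID use in the preceding 72 h there. SAP Listing 16.10 looks back only 24 h, so it would need a longer look-back to display that record.

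The cost is about three NSAID-free days before Visit 17, one of which the 24 h rule already requires, and a one-line amendment. Under Protocol 11.3 the amendment needs sponsor, IRB/IEC and health authority approval, and it can wait for the next one. The change removes the washout mismatch only; Visit 17 will still differ from Visits 11, 13 and 15 in time since injection, and the report should say so.
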